## **9.6 Clinical symptom endpoints based on data collected at site visits**

### **9.6.1 Change from baseline to Month 6 in the subject's rating of item 5 score of the BPI-SF ("pain on the average in the last 24 hours")**

Using the data collected at baseline and Month 6, the change from baseline to Month 6 will be calculated as the difference (Month 6 – baseline). In addition, the percent change from baseline to Month 6 will be calculated as  $100 \times (\text{Month 6} - \text{baseline}) / \text{baseline}$ .

The values collected during the study will be mapped to protocol visits according to the windowed times described in [Table 5](#).

### **9.6.2 Change from baseline to Month 6 in the total score of the subject's rating of item 9 of the BPI-SF (7 pain interference questions: "general activity", "mood", "walking ability", "normal work", "relation with other people", "sleep", "enjoyment of life")**

Using the data collected at baseline and Month 6, the total score at baseline and the total score at Month 6 will be derived as the sum of the 7 questions.

If one question or more is unanswered the total score will be missing. The change from baseline to Month 6 will be calculated as the difference (total score at Month 6 – total score at baseline).

The values collected during the study will be mapped to protocol visits according to the windowed times described in [Table 5](#).

### **9.6.3 Change from baseline to Month 6 in the subject's rating of severity of neuropathic pain as measured by the PGIS-P**

The change in severity of neuropathic pain from baseline to Month 6 will be calculated as the PGIS-P value observed at Month 6 minus the baseline value.

Subjects with a negative change from baseline (change in PGIS-P < 0) will be considered as “improvement”, while a change  $\geq 0$  will be considered as “no improvement”.

The values collected during the study will be mapped to protocol visits according to the windowed times described in [Table 5](#).

#### **9.6.4 Subject rating of change in neuropathic pain severity since study treatment start as measured by the PGIC-PS at Month 6**

Three response variables (yes/no), each corresponding to a different level of improvement, will be defined using the observed data at Month 6:

- “minimally improved” or better (Response = Yes for PGIC-PS = 1, 2 or 3; Response = No for PGIC-PS > 3);
- “much improved” or better (Response = Yes for PGIC-PS = 1 or 2; Response = No for PGIC-PS > 2);
- “very much improved” (Response = Yes for PGIC-PS = 1; Response = No for PGIC-PS > 1).

The values collected during the study will be mapped to protocol visits according to the windowed times described in [Table 5](#).

#### **9.6.5 Change from baseline to Month 6 in the subject’s rating of disease severity as measured by the PGIS-D**

The change in severity of disease from baseline to Month 6 will be calculated as the PGIS-D value observed at Month 6 minus the baseline value.

Subjects with a negative change from baseline (change in PGIS-D < 0) will be considered as “improvement”, while a change  $\geq 0$  will be considered as “no improvement”.

The values collected during the study will be mapped to protocol visits according to the windowed times described in [Table 5](#).

#### **9.6.6 Subject rating of change in disease severity since study treatment start as measured by the PGIC-DS at Month 6**

Three response variables (yes/no), each corresponding to a different level of improvement, will be defined using the observed data at Month 6 using the approach described for PGIC-PS in Section [9.6.4](#).

The values collected during the study will be mapped to protocol visits according to the windowed times described in [Table 5](#).

#### **9.6.7 Change from baseline to Month 6 in the total score of the subject’s rating of the CESD-R-20**

Using the data collected at baseline and Month 6, the total score at baseline and the total score at Month 6 will be derived as the sum of the 20 questions. In order to make the revised

CESD-R have the same range as the original version (i.e., the ‘CESD style score’), the values for the top two responses are given the same value (i.e., answers with the value 4 are given the value 3). As in the original CESD, the range of possible scores is between 0 and 60.

The values collected during the study will be mapped to protocol visits according to the windowed times described in [Table 5](#).

If one question or more is unanswered the total score will be missing. The change from baseline to Month 6 will be calculated as the difference (total score at Month 6 – total score at baseline).

Since a total score  $\geq 16$  indicates a person at risk of clinical depression, a variable for change in risk of depression between baseline and Month 6 will be defined as decreased risk (at risk at baseline, not at risk at Month 6), no change (at risk at baseline and Month 6 or not at risk at baseline and Month 6), increased risk (not at risk at baseline, at risk at Month 6).

In addition to the binary classification of the total score ( $<16$ ,  $\geq 16$ ), the 5-level classification will also be derived [[Radloff 1977](#)]:

- Meets criteria for major depressive episode: anhedonia or dysphoria nearly every day for the past two weeks (defined as at least 1 question out of 2, 4, 6, 8 and 10 answered “nearly every day for 2 weeks”), plus symptoms in an additional 4 DSM symptom groups noted as occurring nearly every day for the past two weeks (defined as at least 1 question answered “nearly every day for 2 weeks” in at least 4 additional symptom groups);
- Probable major depressive episode: anhedonia or dysphoria nearly every day for the past two weeks (defined as above), plus symptoms in an additional 3 DSM symptom groups reported as occurring either nearly every day for the past two weeks, or 5–7 days in the past week (defined as at least 1 question answered “5–7 days” or “nearly every day for 2 weeks” in at least 3 additional symptom groups) without meeting the criteria for major depressive episode;
- Possible major depressive episode: anhedonia or dysphoria nearly every day for the past two weeks (defined as above), plus symptoms in an additional 2 DSM symptom groups reported as occurring either nearly every day for the past two weeks, or 5–7 days in the past week (defined as at least 1 question answered “5–7 days” or “nearly every day for 2 weeks” in 2 additional symptom groups);
- Subthreshold depression symptoms: total CESD-style score of at least 16 without meeting the above criteria;
- No clinical significance: total CESD-style score of less than 16 across all 20 questions without meeting above criteria.

### **9.7 Treatment failure from baseline up to Month 6**

The time to treatment failure up to Month 6 will be defined as the time between randomization and the earliest of the following:

- The date of ERT initiation or re-initiation;
- The date of permanent study treatment discontinuation for any reason.

Subjects who initiated ERT or permanently discontinued study treatment for any reason will be considered as “treatment failure” (event) while other subjects will be censored at their date of last visit performed up to Month 6.

The time to treatment failure will be expressed in months and derived as [Date – Date of randomization] in days / (365.25/12).

## **10 SAFETY VARIABLES**

For determination of treatment-emergent events, the safety analysis will retain the AEs with an onset date between the start of treatment date (included, provided that AE onset is not prior to first dose of study treatment, i.e., AE.AESTRTPT is different from BEFORE) and EOT + 30 days (included). AEs with missing or incomplete onset date compatible with being between the start of treatment date (included, provided that AE onset is not prior to first dose of study treatment, i.e., AE.AESTRTPT is different from BEFORE) and EOT + 30 days (included) will be considered treatment emergent.

For determination of treatment-emergent events, the safety analysis will retain the laboratory values, vital signs, and ECGs with a sampling or assessment date between the start of treatment date (excluded) and EOT + 30 days (included). The baseline value will be taken as the last value available up to the start of treatment date (included).

All laboratory, vital signs and ECG data are taken into account regardless of whether they correspond to scheduled or unscheduled assessments.

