3.1.1 Study periods

The study comprises the following consecutive periods:

Screening period: Lasts approximately 6–7 weeks; starts with the signing of the informed consent form (ICF; at the screening visit) and ends the day before subject randomization.

Treatment period: Lasts approximately 6 months. Starts on the day of subject randomization (randomization visit) and ends at the EOT visit (Month 6). It will consist of site visits at Month 1, Month 3, Month 5 and Month 6 and telephone call visits at Month 2 and Month 4.

The EOT visit will take place at Month 6 (or earlier in the event of premature discontinuation).

Whenever possible, the EOT visit should take place 1 day after the last dose of study treatment but no later than 7 days after the last dose of study treatment.

Post-treatment observation period (PTOP): Subjects who discontinue study treatment prematurely will enter into the PTOp, which starts on the day after the last dose of study treatment, and ends at latest at the Month 6 PTOp visit.

During this period, all assessments except PK will be performed. They will be performed at the time of the originally scheduled visits [[Table 6](#)].

Post-treatment safety follow-up (FU) period: The FU period is applicable to all subjects except those who enter the open-label extension (OLE) study. It starts on the day after the last dose of study treatment:

- For female and non-fertile male subjects: it includes 1 safety FU telephone call (FU1) taking place approximately 1 month after the last dose of study treatment;
- For fertile male subjects: it includes 2 safety FU telephone calls taking place approximately 1 month (FU1) and 3 months (FU2) after the last dose of study treatment.

Subjects who complete the 6-month double-blind treatment period will be proposed to enroll into an OLE study conducted under a separate protocol (provided the OLE study protocol has been approved in the country/site by regulatory authorities and Ethics Committees [ECs] / Institutional Review Boards [IRBs]).

Subjects who discontinue study treatment prematurely for any reason should be subsequently treated according to local standard-of-care at the investigator's discretion and will be followed in the PTOp until the originally scheduled Month 6 visit.

[figure not shown]
For an individual subject, the End-of-Study (EOS) is defined as follows:

- For subjects who enter the OLE study, the EOS corresponds to the EOT visit;

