9.3 Reporting procedures

9.3.1 Reporting of adverse events

All AEs with an onset date after signing of the ICF and up to 30 days after study treatment discontinuation or up to the last visit of the PTOP period (whichever is the latest) must be recorded on specific AE forms of the eCRF.

Information to be collected in an AE form in the eCRF includes date of onset, action taken with the study treatment, outcome of AE, date of resolution (if applicable) and PI's assessment of intensity, and relationship to study treatment, study design or protocol mandated procedures.

Information on worsening of intensity will be collected on a new AE form. If the AE lessens in intensity, no change in the severity is required to be reported.

Follow-up information on ongoing AE obtained after the subject's EOS visit will not be collected in the eCRF.

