10.2.3 Safety variables

The variables described in this section are to be used for the derivation of the safety endpoints described in Section 6.2.

Treatment-emergent laboratory values, vital signs or AEs are those with an assessment or onset date/time \geq start date/time of study treatment and \leq 30 days after study treatment discontinuation.

Abnormalities for laboratory, vital signs and ECGs will be defined in the SAP.

Laboratory analyses are based on data received from the central laboratory as well as local laboratories.

All laboratory, vital signs and ECG data are taken into account regardless of whether they correspond to scheduled or unscheduled assessments.

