## 5 GENERAL DEFINITIONS AND DERIVATIONS

### 5.1 Dates

‘**Randomization date**’ is taken from the date of the randomization visit (V2) recorded in the eCRF. Subjects for whom the date of the randomization visit does not match the date recorded in the IRT system will be listed.

The ‘**Start of treatment date / First study treatment intake date**’ is defined as the date the first dose of study treatment was received (lucerastat or placebo) as documented in the eCRF study treatment log.

The ‘**EOT date**’ is defined as the date of the last dose of study treatment intake as documented in the eCRF study treatment log. In case of incomplete date of the last dose of study treatment intake in the study treatment log of a subject having reached EOS, the EOT

date will be imputed with the latest possible date compatible with the incomplete date, while not being later than EOS.

The ‘EOS date’ will be taken from the eCRF end of study status form. If this date is missing, the last recorded visit or telephone call on the eCRF is considered as the EOS date.

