**Table 15 Time windows for all assessments up to EOT + 30 days**

Visit	Treatment day (nominal value)	Lower limit treatment day	Upper limit treatment day
Month 1	30	2	45
Month 2	61	46	75
Month 3	91	76	106
Month 4	122	107	136
Month 5	152	137	167
Month 6	183	168	EOT + 30

Should more than one assessment fall within the same time window, then the closest value to the planned treatment day will be assigned to the visit. In the event of values that are equidistant to the planned treatment day, the latest assessment will be retained.

Where more than one assessment falls on the same day, the first available central assessment is used.

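### The treatment-emergent AE window has no cut-off at entry to the open-label extension, so an AE that starts on open-label lucerastat could be counted under placebo

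*SAP*

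**What the plan says.** On the analysis window:

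- SAP section 10: "the safety analysis will retain the AEs with an onset date between the start of treatment date" and EOT + 30 days. Laboratory values, vital signs and ECGs have the same end. For AEs with a missing or partial onset date, those compatible with a date up to "EOT + 30 days (included) will be considered treatment emergent".
- SAP section 5.1: the EOT date "is defined as the date of the last dose of study treatment intake as documented in the eCRF study treatment log", that is, the last double-blind dose.
- Protocol section 10.2.3 sets the same limit for AEs, laboratory values and vital signs: "30 days after study treatment discontinuation".
- SAP Table 15, titled "Time windows for all assessments up to EOT + 30 days", closes the Month 6 window for visit summaries at the same point.

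On data collection:

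- Protocol section 9.3.1 requires entry in the eCRF of "All AEs with an onset date after signing of the ICF and up to 30 days after study treatment discontinuation", or to the last PTOP visit if that is later. Section 9.3.2 sets the same period for SAEs. Neither exempts extension entrants.
- Protocol section 3.1.1: "The FU period is applicable to all subjects except those who enter the open-label extension (OLE) study". The same section adds: "For subjects who enter the OLE study, the EOS corresponds to the EOT visit". SAP section 2.1 repeats both rules.

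Neither document ends the treatment-emergent window at EOS or at the first extension dose, and neither assigns events after extension entry to another group.

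**The concern.** Where the extension protocol is approved, every completer is offered the extension, and protocol sections 6.1.4.1 and 6.1.4.2 tie it to lucerastat. A placebo subject who rolls over can therefore start active drug inside the 30-day tail of the placebo window. An AE that begins then, if it is in this study's database, would be tabulated under placebo. Early-onset effects of lucerastat would be the ones most likely to land in the wrong column. Safety and tolerability is a stated secondary objective, and the placebo arm is small, so a few misplaced subjects would be visible in the AE percentages.

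**Working it through.** The plan gives no figure on this point to reproduce. The check is a reading of the rules, followed by a sizing of the window.

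**Rules side by side, for a placebo subject who rolls over**

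| Question | Source | Answer |
|---|---|---|
| When does the treatment-emergent window end? | SAP 10; protocol 10.2.3 | 30 days after the last double-blind dose |
| How long are AEs and SAEs recorded here? | Protocol 9.3.1, 9.3.2 | 30 days after stopping study drug |
| When does the subject's study end? | Protocol 3.1.1; SAP 2.1 | At the EOT visit, ideally 1 day and at most 7 days after the last dose |
| Are FU1 and FU2 calls made? | Protocol 3.1.1; Table 5 footnote b | No |
| In which column is the subject counted? | SAP 4.1.6 | By treatment received. Accidental dispensing of both treatments is covered; planned rollover is not |

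The first two rows let an AE that starts in the extension reach the placebo column. The third and fourth suggest that it would not be collected. Protocol section 9.3.1 does not settle this: what it excludes after EOS is follow-up information on AEs already ongoing, and it is silent on new ones. SAP section 7.7, by contrast, does stop study-concomitant medications at EOS, so a cut at EOS is used elsewhere in the same document.

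**Length of window exposed**

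Inputs: nominal Month 6 day 183 (SAP Table 5), 30-day tail (SAP 10), about 39 placebo subjects (SAP 2). Assumptions: extension dosing starts 0 to 7 days after the last double-blind dose, and 50% to 100% of placebo subjects roll over.

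- Days on extension drug per placebo rollover = 30 − gap: 30 − 7 = 23 to 30 − 0 = 30.
- Share of the window = days / (183 + 30): 23/213 = 10.8% to 30/213 = 14.1%.
- Subject-years = subjects × days / 365.25: 19.5 × 23 / 365.25 = 1.2 to 39 × 30 / 365.25 = 3.2.
- Weight of one misplaced subject in a placebo percentage: 1/39 = 2.6 percentage points.

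These figures give the reach of the window. They do not give a number of events, because the documents state no rollover rate, extension start date or AE rate.

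**Which data are exposed**

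Protocol Table 5 schedules no laboratory test, vital sign or ECG after the EOT visit for rollovers, and allows unscheduled visits only until EOS. The exposure is therefore mainly to AEs and SAEs.

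**With the window cut at EOS**

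If extension dosing starts at or after the EOT visit, the days on extension drug fall from 23 to 30 to none, apart from the visit day itself. Post-dose AE observation is then at most about 7 days for rollovers and 30 days for others.

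**The case against.** The strongest reply is that these events never enter this study. Protocol section 9.1.1 confines AEs to those arising while the study is under way, and for rollovers the study ends at the EOT visit. The follow-up calls are skipped for them. Under section 3.1.2, if the last subject rolls over, the whole study ends at that subject's EOT visit, so collecting AEs for 30 more days would run past the study's own end. The extension has its own protocol.

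This largely stands. A reader might infer from SAP section 10 alone that AEs starting on open-label lucerastat will be counted as placebo events and will mask harm. The documents do not support that: it happens only if such AEs are recorded here, and the rules on that disagree. A reader might also try to size the masking. Suppose 10% of subjects have an AE in the first month on lucerastat and 0% on placebo, and 50% to 100% of placebo subjects roll over. Placebo would then show 5% to 10%, and a 10-point difference would read as 0 to 5 points. Every one of those inputs is assumed, so this is not an estimate for this trial.

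The reply does not remove the conflict. Sections 9.3.1 and 9.3.2, read on their own, tell a site to keep recording for 30 days, and SAP section 10 would count whatever was recorded.

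A second reply is that if collection does stop at EOS, the shorter tail for rollovers does little harm. Protocol section 1.2.3 reports half-lives of 3.6 to 16.9 hours after single doses in healthy subjects and 16.1 hours in severe renal impairment, so most of the days lost are off drug. This is fair. No distortion between arms is shown from unequal tails, and a note with the tables is enough.

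**Conclusion.** The point holds as a gap in the rules, not as a demonstrated bias. The treatment-emergent window runs to EOT + 30 days for everyone with no cut-off at extension entry, and the collection rules for extension entrants contradict each other. Any AE or SAE recorded here with onset after a placebo subject starts open-label lucerastat would be counted under placebo.

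The effect could be nil, if sites stop recording at the EOT visit. At the other end, 1.2 to 3.2 subject-years of the placebo window would lie on extension drug under the stated assumptions on rollover and start date. That the extension drug is lucerastat is implied by the protocol; its dosing and timing are not in these documents. Laboratory, vital-sign and ECG summaries are hardly touched. The case for acting rests on the low cost of the correction.

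**What to change.** Before unblinding, add to SAP section 10: *for a subject who enters the open-label extension, the treatment-emergent window ends at the earlier of EOT + 30 days and the EOS date (the EOT visit); AEs recorded with a later onset are listed separately and not tabulated.* Apply the same end to the rule for partial onset dates, and say whether the EOS day itself is included, since extension dosing might begin that day.

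The EOS date is already taken from the eCRF (SAP section 5.1), so no new data are needed. Subjects outside the extension who have their FU1 call at 30 to 37 days after the last dose (protocol Table 5) reach EOS no earlier than EOT + 30 days and keep their full window. Table 15 can stay as it is, because rollovers have no scheduled assessments after EOS.

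The small downside is the unequal tail: at most about 7 days of post-dose AE observation for rollovers against 30 for others. A footnote to the AE tables should say so. A protocol amendment is not needed, as the SAP describes randomization as complete. Nor is an exposure-adjusted column, as SAP section 14.5 already reports subject-years of exposure.

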### **10.1 Adverse events**

- Treatment-emergent AEs;
- Treatment-emergent serious AEs (SAEs);
- AEs leading to permanent discontinuation of study treatment.

### **10.2 Laboratory data**

- Change from baseline to each visit up to Month 6;
- Treatment-emergent marked abnormalities;

Laboratory analyses are based on data received from the central laboratory as well as local laboratories. The laboratory parameters considered as safety parameters are the following:

### **Hematology**

- Hemoglobin (g/L);
- Hematocrit (%);
- Erythrocyte count ( $10^{12}/L$ );
- Reticulocyte count ( $10^9/L$ );
- Leukocyte count ( $10^9/L$ );
- Neutrophils ( $10^9/L$ ), lymphocytes ( $10^9/L$ ), monocytes ( $10^9/L$ ), eosinophils ( $10^9/L$ ), basophils ( $10^9/L$ );
- Platelet count ( $10^9/L$ ).

### **Blood chemistry**

- Alanine aminotransferase (U/L), aspartate aminotransferase (U/L), alkaline phosphatase (U/L);
- Bilirubin ( $\mu\text{mol}/L$ );
- Direct bilirubin ( $\mu\text{mol}/L$ );
- Creatinine ( $\mu\text{mol}/L$ );
- eGFR ( $\text{mL}/\text{min}/1.73 \text{ m}^2$ );
- Urea nitrogen ( $\text{mmol}/L$ );
- Urate ( $\mu\text{mol}/L$ ; labelled “Uric acid” in source data);
- Albumin (g/L), Protein (g/L);
- Glucose ( $\text{mmol}/L$ ), HbA1c (%);
- Cholesterol ( $\text{mmol}/L$ ), triglycerides ( $\text{mmol}/L$ );
- Sodium, potassium, chloride, calcium ( $\text{mmol}/L$ );
- N-terminal pro-brain natriuretic peptide ( $\text{pg}/\text{mL}$ ;  $\text{pg}/\text{mL}$  is same as  $\text{ng}/L$ ).

